15.1.2.20 Section 9.6.3.7 Safety laboratory tests

This section was changed as a result of Modification 15.1.1.3.

Old text:

Only blood samples analyzed at the central laboratory will be considered for analysis. The name and address for the central lab service provider can be found in the documentation supplied by the vendor. The safety laboratory tests may be repeated once during the screening period if laboratory values are outside the inclusion range and assessed as clinically relevant.

New text:

Only blood samples analyzed at the central laboratory will be considered for analysis. The name and address for the central lab service provider can be found in the documentation supplied by the vendor. For a given laboratory parameter, the acceptable values for inclusion would consist of values within the reference ranges, measured at baseline, as provided in the Covance Central Laboratory Services (CCLS) Manual for Bayer Protocol 18649 (Covance Project #: 518179). The safety laboratory tests may be repeated once during the screening period if laboratory values are outside the inclusion range and assessed as clinically relevant.

15.1.2.21 Section 9.6.3.8 Presence of Mirena removal threads

This section was changed as a result of Modification 15.1.1.22.

Old text:

[...]

The investigator will perform pelvic examinations at each study visit to verify the presence of the Mirena removal threads in the appropriate location in the cervical os. ~~At the investigator's discretion, transvaginal ultrasound (TVUS) may be performed to verify that the Mirena is in the appropriate intrauterine location and to exclude expulsion or perforation.~~ [...]

New text:

[...]

The investigator will perform pelvic examinations at each study visit to verify the presence of the Mirena removal threads in the appropriate location in the cervical os. If the presence of the removal threads cannot be verified, transvaginal ultrasound (TVUS) is to be performed to verify that the Mirena is in the appropriate intrauterine location and to exclude expulsion or perforation. [...]

15.1.2.22 Section 9.6.3.12 Uterine bleeding

This section was changed as a result of Modification 15.1.1.19.

Old text

Table 9-3 Uterine bleeding – bleeding intensity definitions

Category	Intensity	Definition
None	None	No uterine bleeding
Spotting	Spotting	Less than associated with normal menstruation relative to the woman's experience, with no need for sanitary protection except for panty liners
Bleeding	Light	Less than associated with normal menstruation relative to the woman's experience, with need for sanitary protection
	Normal	Like normal menstruation relative to the woman's experience
	Heavy	More than normal menstruation relative to the woman's experience

New text:

Table 9-3 Uterine bleeding – bleeding intensity definitions

Category	Intensity	Bleeding Intensity Code	Definition
None	None	1	No uterine bleeding
Spotting	Spotting	2	Less than associated with normal menstruation relative to the woman's experience, with no need for sanitary protection except for panty liners
Bleeding	Light	3	Less than associated with normal menstruation relative to the woman's experience, with need for sanitary protection
	Normal	4	Like normal menstruation relative to the woman's experience
	Heavy	5	More than normal menstruation relative to the woman's experience

15.1.2.23 Section 9.7.1 eDiary

This section was changed as a result of Modification 15.1.1.23.

Old text:

[...]

The use of the eDiary will be explained in detail in a site manual, and the site personnel will train the subject on how to use the device at the baseline visit. At all the following visits (see Table 9-1), the eDiary entries will be checked and documented by the study site personnel for completeness. [...]

New text:

[...]

Subject will enter her data daily into the eDiary. The use of the eDiary will be explained in detail in a site manual, and the site personnel will train the subject on how to use the device at the baseline visit. At all the following visits (see Table 9-1), the eDiary entries will be checked and documented by the study site personnel for completeness. [...]

15.1.2.24 Section 9.7.4 Subject satisfaction with Mirena

This section was changed as a result of Modification 15.1.1.1.

Old text:

At baseline visit, visit 6 and at the end of the treatment (EOT, visit 8) (see also Table 9-1), the subject is asked to evaluate her satisfaction with the Mirena on a 5-point scale as very satisfied, somewhat satisfied, neither satisfied or dissatisfied, dissatisfied or very dissatisfied. Information regarding the subject satisfaction will be documented by the investigator in eCRF.

New text:

At baseline visit, visit 4, 6 and at the end of the treatment (EOT, visit 8) (see also Table 9-1), the subject is asked to evaluate her satisfaction with the Mirena on a 5-point scale as very satisfied, somewhat satisfied, neither satisfied or dissatisfied, dissatisfied or very dissatisfied. Information regarding the subject satisfaction will be documented by the investigator in eCRF.

15.1.2.25 Section 10.2 Analysis sets

This section was changed as a result of Modification 15.1.1.1, 15.1.1.18 and 15.1.1.25.

Old text:

The documentation of important deviations and the assignment of subjects to analysis sets will be performed according to the ~~sponsor's~~ applicable Standard Operating Procedures and/or Instruction Manuals.

The following statistical analysis sets will be defined:

Full analysis set (FAS):

All women who completed the baseline visit of the study

Primary analysis set Year 7 (PAS year 7):

All women in the FAS with an age of 34 years or younger at baseline visit (i.e., an age of 36 or younger at end of year 7)

Primary analysis set Year 8 (PAS year 8):

All women in the FAS with an age of 33 years or younger at baseline visit (i.e., an age of 36 or younger at end of year 8)

Safety analysis set (SAF):

All women who completed the baseline visit of the study, analyzed for the FAS

The age at baseline (required for PAS year 7 and PAS year 8) will be ~~approximated as the difference between year of baseline visit and year of birth recorded at screening visit.~~

New text:

The documentation of important deviations and the assignment of subjects to analysis sets will be performed according to the CRO's applicable Standard Operating Procedures and/or Instruction Manuals.

The following statistical analysis sets will be defined:

Full analysis set (FAS):

All women who completed the baseline visit of the study

Primary analysis set Year 6 (PAS year 6):

All women in the FAS with an age of 35 years or younger at baseline visit (i.e., an age of 36 or younger at end of year 6)

Primary analysis set Year 7 (PAS year 7):

All women in the FAS with an age of 34 years or younger at baseline visit (i.e., an age of 36 or younger at end of year 7)

Primary analysis set Year 8 (PAS year 8):

All women in the FAS with an age of 33 years or younger at baseline visit (i.e., an age of 36 or younger at end of year 8)

Safety analysis set (SAF):

All women who completed the baseline visit of the study, analyzed for the FAS

The age at baseline (required for PAS year 6, PAS year 7 and PAS year 8) will be used as recorded at the baseline visit 2.

15.1.2.26 Section 10.3 Variables and planned statistical analyses

This section was changed as a result of Modification 15.1.1.26.

New text added (no old text):

In order to allow some flexibility, the baseline visit is planned to take place 14 to 0 days before the end of Year 5 of Mirena use (see Table 9-1). As a consequence, it is expected there will be various subjects with that baseline visit taking place prior to the start of 'extension treatment period', i.e. Day 1 of Year 6 of Mirena use.

Variables collected on an ongoing basis will primarily be analyzed for the 'extension treatment period' starting at Day 1 of Year 6 of Mirena use, i.e., data collected between the baseline visit and Day 1 of Year 6 of Mirena use will be excluded:

- Primary efficacy variable, i.e. occurrence of pregnancies (section 10.3.2.1)

- Main safety variable, i.e. adverse events (section 10.3.2.3.1)
- Uterine bleeding / bleeding pattern (section 10.3.2.3.2)

Variables collected at pre-specified visits/timeframes only will be analyzed per visit (unless otherwise stated):

- Secondary efficacy variable, i.e. menstrual blood loss (section 10.3.2.2)
- Other safety variables, not listed above (section 10.3.2.3)
- Other variables (section 10.3.2.4)

More details will be provided in the statistical analysis plan.

15.1.2.27 Section 10.3.1.1.1 Primary efficacy variable

This section was changed as a result of Modifications 15.1.1.1 and 15.1.1.26.

Old text:

The primary efficacy variable is the occurrence of pregnancy within years 6 thru 8 of Mirena use. However, for the analysis after 7 years, the primary efficacy variable is the occurrence of pregnancy within years 6 thru 7 of Mirena use.

The PI is defined as the number of pregnancies per 100 woman years. The following PIs will be calculated:

- 'Two years PI (sixth & seventh year)', PI obtained in the sixth and seventh year of treatment, i.e., number of pregnancies that occurred during the sixth and seventh year of treatment divided by time the women were under risk of getting pregnant in the sixth and seventh year of treatment.
- 'Three years PI (sixth, seventh & eighth year)', PI obtained in the sixth, seventh and eighth year of treatment, i.e., number of pregnancies that occurred during the sixth, seventh and eighth year of treatment divided by time the women were under a risk of getting pregnant in the sixth, seventh and eighth year of treatment.
- 'Overall PI', PI obtained during the whole study, i.e., number of pregnancies that occurred during the ~~studied treatment period beyond 5 years~~ divided by the time the women were under a risk of getting pregnant.

New text:

The primary efficacy variable is the occurrence of pregnancy within years 6 thru 8 of Mirena use. However, for the analysis after 6 years of Mirena use, the primary efficacy variable is the occurrence of pregnancy within year 6 of Mirena use, and for the analysis after 7 years, the primary efficacy variable is the occurrence of pregnancy within years 6 thru 7 of Mirena use.

The PI is defined as the number of pregnancies per 100 woman years. The Pearl Index will be analyzed for the 'extension treatment period' starting at Day 1 of Year 6 of Mirena use, i.e.,

exposure and pregnancies between the baseline visit and Day 1 of Year 6 of Mirena use will be excluded. The following PIs will be calculated:

- '1-year PI' (sixth year)', PI obtained in the sixth year of treatment, i.e., number of pregnancies that occurred during the sixth year of treatment divided by time the women were under risk of getting pregnant in the sixth year of treatment.
- '2-year PI (sixth & seventh year)', PI obtained in the sixth and seventh year of treatment, i.e., number of pregnancies that occurred during the sixth and seventh year of treatment divided by time the women were under risk of getting pregnant in the sixth and seventh year of treatment.
- '3-year PI (sixth, seventh & eighth year)', PI obtained in the sixth, seventh and eighth year of treatment, i.e., number of pregnancies that occurred during the sixth, seventh and eighth year of treatment divided by time the women were under a risk of getting pregnant in the sixth, seventh and eighth year of treatment.

Furthermore, the following PI will be analyzed for the entire study period starting at baseline visit, i.e., exposure and pregnancies between the baseline visit and Day 1 of Year 6 of Mirena use will be included:

- 'Overall PI', PI obtained during the whole study, i.e., number of pregnancies that occurred during the entire study period starting at baseline visit divided by the time the women were under a risk of getting pregnant.

15.1.2.28 Section 10.3.1.2 Safety variables

This section was changed as a result of Modification 15.1.1.15 and 15.1.1.26.

Old text:

The main safety variable is the incidence of ~~post-baseline~~ adverse events (both serious and non-serious).

Other safety variables are:

- Uterine bleeding / Bleeding pattern
- Vital signs and weight
- ~~Physical examination~~
- ~~Gynecological examination~~

[...]

New text:

The main safety variable is the incidence of treatment-emergent adverse events (both serious and non-serious). Treatment-emergent AEs are defined as any AEs occurring during the 'extension treatment period' starting at Day 1 of Year 6 of Mirena use.

Other safety variables are:

- Uterine bleeding / Bleeding pattern
- Vital signs and weight

[...]

15.1.2.29 Section 10.3.2.1 Analysis of the primary variable

This section was changed as a result of Modification 15.1.1.1, 15.1.1.5, 15.1.1.7, 15.1.1.8, 15.1.1.9 and 15.1.1.26.

Old text:

The primary variable is the occurrence of pregnancy within years 6-8 of Mirena use. However, for the analysis after 7 years, the primary variable is the occurrence of pregnancy within years 6 thru 7 of Mirena use.

New text:

The primary variable is the occurrence of pregnancy within years 6-8 of Mirena use. However, for the analysis after 6 years, the primary variable is the occurrence of pregnancy within years 6 of Mirena use, and for the analysis after 7 years, the primary variable is the occurrence of pregnancy within years 6 thru 7 of Mirena use.

[...]

Old text:

Table 10–1 Definition of crude exposure times

PI	Reason for end of study/ continuation status	Crude exposure time
Two-years PI (sixth & seventh year)	Total expulsion	Date, when expulsion was realized – Baseline visit date +1
	Partial Expulsion/ Mirena removal	Date of Mirena removal – Baseline visit date +1
	Pregnancy	Date of conception – Baseline visit date +1
	Lost to Follow up	Max (Date Mirena last known in situ – Baseline visit date +1, 0)
	Continues into 8th year of 730 days treatment	
Three-years PI (sixth, seventh & eighth year)	Total expulsion	Date, when expulsion was realized – Baseline visit date +1
	Partial Expulsion/ Mirena removal	Date of Mirena removal – Baseline visit date +1
	Pregnancy	Date of conception – Baseline visit date +1
	Lost to Follow up	Max (Date Mirena last known in situ – Baseline visit date +1, 0)

PI	Reason for end of study/ continuation status	Crude exposure time
	Continues into 9th year of treatment	Min (1095 days, Date of EOT visit – Baseline visit date +1)
Overall PI	Total expulsion	Date, when expulsion was realized – Baseline visit date +1
	Partial Expulsion/ Mirena removal	Date of Mirena removal – Baseline visit date +1
	Pregnancy	Date of conception – Baseline visit date +1
	Lost to Follow up	Max (Date Mirena last known in situ – Baseline visit date +1, 0)
	Continued until EOT	Date of EOT visit – Baseline visit date +1

A pregnancy will be allocated to the time period(s) that are relevant for the calculation of the PIs described above, e.g., a pregnancy that occurs on day 400 will be relevant for the 7th year PI, the two years PI (6th and 7th year), the three years PI (6th, 7th and 8th year), and the overall PI. Pregnancies that occur after the Mirena was removed or an expulsion was realized will not count for any PI.

[...]

Exposure times to be subtracted:

Subjects who apply additional concomitant contraception are not in risk or are under a lower risk of getting pregnant than subjects who do not apply additional contraception. In case a subject uses concomitant contraceptive methods (e.g., condoms to prevent STD) the period of additional contraceptive method use will be excluded from the exposure time.

[...]

The primary analysis set will be the PAS year 7 (for the analysis after 7 years) and the PAS year 8 (for the final analysis after 8 years), respectively. Furthermore, analyses will be repeated for the FAS.

New text:

Table 10–1 Definition of crude exposure times – amended

PI	Reason for end of study/ continuation status	Crude exposure time
1-year PI (6th year)	Total expulsion	Date, when expulsion was discovered – Date of Day 1 Year 6 +1
	Partial Expulsion/ Mirena removal	Date of Mirena removal – Date of Day 1 Year 6 +1
	Pregnancy	Date of conception – Date of Day 1 Year 6 +1
	Lost to Follow up	Maximum of (Date Mirena last known in situ – Date of Day 1 Year 6 +1; 1 day)
	Continues into 7th year of treatment	365 days
2-year PI (6th and 7th year)	Total expulsion	Date, when expulsion was discovered – Date of Day 1 Year 6 +1
	Partial Expulsion/ Mirena removal	Date of Mirena removal – Date of Day 1 Year 6 +1
	Pregnancy	Date of conception – Date of Day 1 Year 6 +1
	Lost to Follow up	Maximum of (Date Mirena last known in situ – Date of Day 1 Year 6 +1; 1 day)
	Continues into 8th year of treatment	730 days
3-year PI (6th, 7th and 8th year)	Total expulsion	Date, when expulsion was discovered – Date of Day 1 Year 6 +1
	Partial Expulsion/ Mirena removal	Date of Mirena removal – Date of Day 1 Year 6 +1
	Pregnancy	Date of conception – Date of Day 1 Year 6 +1
	Lost to Follow up	Maximum of (Date Mirena last known in situ – Date of Day 1 Year 6 +1; 1 day)
	Continues into 9th year of treatment	Minimum of (1095 days; Date of EOT visit – Date of Day 1 Year 6 +1)
Overall PI	Total expulsion	Date, when expulsion was discovered – Baseline visit date +1
	Partial Expulsion/ Mirena removal	Date of Mirena removal – Baseline visit date +1
	Pregnancy	Date of conception – Baseline visit date +1
	Lost to Follow up	Maximum of (Date Mirena last known in situ – Baseline visit date +1; 1 day)
	Continued until EOT	Date of EOT visit – Baseline visit date +1

A pregnancy will be allocated to the time period(s) that are relevant for the calculation of the PIs described above, e.g., a pregnancy that occurs on day 400 will be relevant for the 7th year PI, the two years PI (6th and 7th year), the three years PI (6th, 7th and 8th year), and the overall PI. Pregnancies that occur before Day 1 Year 6 of Mirena use will not count for the 1-year PI, 2-year PI and 3-year PI. Pregnancies that occur after the Mirena was removed or an expulsion was realized will not count for any PI.

[...]

Furthermore, it should be noted that pregnancies that occur within 7 days after the end of exposure will count for the PIs.

Exposure times to be subtracted:

Subjects who apply additional concomitant contraception are not in risk or are under a lower risk of getting pregnant than subjects who do not apply additional contraception. In case a subject uses concomitant contraceptive methods (e.g., condoms to prevent STD) the respective 28-day reference period(s) of additional contraceptive method use will be excluded from the exposure time, unless a pregnancy occurred in that 28-day reference period.

[...]

The primary analysis set will be the PAS Year 6 (for the analysis after 6 years), the PAS Year 7 (for the analysis after 7 years) and the PAS Year 8 (for the final analysis after 8 years), respectively. Furthermore, analyses will be repeated for the FAS.

[...]

15.1.2.30 Section 10.3.2.2.1 Menstrual blood loss

This section was changed as a result of Modification 15.1.1.10.

Old text:

[...]

The basis for this analysis is the data on MBL assessed by the alkaline hematin method (see section 9.4.2). If a woman has documented in the eDiary (see section 9.7.1) that no bleeding occurred during one of the ~~considered~~ 30-day time periods for collection of sanitary ~~protection~~, the MBL will be assumed to be zero in that time period.

This analysis will be conducted in the FAS in the subgroup of women who had Mirena inserted for HMB.

New text:

[...]

The basis for this analysis is the data on MBL assessed by the alkaline hematin method (see section 9.4.2). If a woman has documented in the eDiary (see section 9.7.1) that no bleeding occurred during one of the 30-day time periods considered for collection of sanitary products,

the MBL will be assumed to be zero in that time period. The handling of partial or missing data (i.e. data on sanitary products and/or bleeding intensities) and detailed imputation rules will be described in the statistical analysis plan.

This analysis will be conducted in the FAS in the HMB subgroup, i.e. women who had Mirena inserted for both contraception and HMB.

[...]

15.1.2.31 Section 10.3.2.2.2 Categorized menstrual blood loss (MBL) (<80ml / 30 days)

This section was changed as a result of Modification 15.1.1.11.

Old text:

No clinical change in bleeding profile regarding HMB will be concluded if the volume of blood loss ~~remains~~ < 80mL ~~during~~ the end of years 6, 7 and 8. Therefore, the proportion of women with ~~an MBL <80 mL / 30 days will~~ analyzed. Descriptive statistics as well as 95% Clopper-Pearson confidence intervals will be provided ~~for each of the time periods in which HMB is assessed.~~ Success will be concluded regarding this endpoint if less than 20% of the women ~~included into the study for HMB~~ have a clinical change in bleeding profile (according to the definition above).

This analysis will be conducted in the FAS in the subgroup ~~of~~ women who had Mirena inserted for HMB.

New text:

No clinical change in bleeding profile regarding HMB after Year 5 until the end of Year 6, until the end of Year 7 and until the end of Year 8, respectively, will be concluded if the volume of blood loss was < 80mL at the beginning of Year 6 and remained < 80mL at the end of Years 6, 7 and 8, respectively. Vice versa, clinical change in bleeding profile regarding HMB after Year 5 until the end of Year 6, end of Year 7 and end of Year 8, respectively, will be concluded if the volume of blood loss was \geq 80mL at the beginning of Year 6 or at end of Years 6, 7 or 8, respectively.

Therefore, the proportion of women with clinical change in bleeding profile regarding HMB will be analyzed. Descriptive statistics as well as 95% Clopper-Pearson confidence intervals will be provided.

For the analysis after 6 years, the proportion of women with clinical change in bleeding profile regarding HMB after Year 5 until the end of Year 6 will be analyzed.

For the analysis after 6 years, the following women will constitute the denominator:

- Baseline MBL >80mL/30days, or
- Baseline MBL not >80mL/30days and End of Year 6 MBL assessment available.

That means, women with Baseline MBL not >80mL/30days and MBL assessment at the end of Year 6 not available will be excluded from the denominator, as they are considered lost to follow up without preceding clinical change in bleeding profile regarding HMB.

For the analysis after 6 years, the following women will constitute the nominator:

- Baseline MBL>80mL/30days, or
- End of Year 6 MBL>80mL/30days.

For the analysis after 7 years, the proportion of women with clinical change in bleeding profile regarding HMB **after Year 5 until the end of Year 7** will be analyzed.

For the analysis after 7 years, the following women will constitute the denominator:

- Baseline MBL>80mL/30days, or
- End of Year 6 MBL>80mL/30days, or
- Baseline MBL not >80mL/30days and
End of Year 6 MBL not >80mL/30days and
End of Year 7 MBL assessment available.

That means, women with Baseline MBL not >80mL/30days, MBL at the end of Year 6 not >80mL/30days and MBL assessment at the end of Year 7 not available will be excluded from the denominator, as they are considered lost to follow up without preceding clinical change in bleeding profile regarding HMB.

For the analysis after 7 years, the following women will constitute the nominator:

- Baseline MBL>80mL/30days, or
- End of Year 6 MBL>80mL/30days, or
- End of Year 7 MBL>80mL/30days.

For the final analysis after 8 years, the proportion of women with clinical change in bleeding profile regarding HMB **after Year 5 until the end of Year 8** will be analyzed.

For the analysis after 8 years, the following women will constitute the denominator:

- Baseline MBL>80mL/30days, or
- End of Year 6 MBL>80mL/30days, or
- End of Year 7 MBL>80mL/30days, or
- Baseline MBL not >80mL/30days and
End of Year 6 MBL not >80mL/30days and
End of Year 7 MBL not >80mL/30days and
End of Year 8 MBL assessment available.

That means, women with Baseline MBL not >80mL/30days, MBL at the end of Year 6 not >80mL/30days, MBL at the end of Year 7 not >80mL/30days and MBL assessment at the end of Year 8 not available will be excluded from the denominator, as they are considered lost to follow up without preceding clinical change in bleeding profile regarding HMB.

For the analysis after 8 years, the following women will constitute the nominator:

- Baseline MBL>80mL/30days, or
- End of Year 6 MBL>80mL/30days, or
- End of Year 7 MBL>80mL/30days, or
- End of Year 8 MBL>80mL/30days.

Success will be concluded regarding this endpoint if less than 20% of the women in the HMB subgroup have a clinical change in bleeding profile regarding HMB (according to the definition above) and the upper limit of the corresponding 95% Clopper-Pearson confidence interval is equal to or less than 35%.

This analysis will be conducted in the FAS in the HMB subgroup, i.e. women who had Mirena inserted for both contraception and HMB.

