10.3.1.1.2 Secondary efficacy variables

Secondary efficacy variables are:

- Menstrual blood loss (MBL) during a 30-day period starting at the baseline visit and at the end of Years 6, 7 and 8. MBL will be measured by the alkaline hematin method. The assessment of this variable is restricted to women who had Mirena inserted for HMB.
- Categorized menstrual blood loss (MBL) (≥ 80 ml per 30 days) at end of Year 6, 7 and 8. The assessment of this variable is restricted to women who had Mirena inserted for HMB.

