6.2.2.2 Categorized menstrual blood loss (<80 mL / 30 days)

No clinical change in bleeding profile regarding HMB after Year 5 until the end of Year 6, until the end of Year 7 and until the end of Year 8, respectively, will be concluded if the cumulative volume of MBL was < 80mL at the beginning of Year 6 and remained remains <80mL during the end of years 6, 7 and 8, respectively. Vice versa, clinical change in bleeding profile regarding HMB after Year 5 until the end of Year 6, end of Year 7 and end of Year 8, respectively, will be concluded if the volume of blood loss was ≥ 80mL at the beginning of Year 6 or at end of Years 6, 7 or 8, respectively.

Therefore, the proportion of women with clinical change in bleeding profile regarding HMB will be analyzed. Descriptive statistics as well as 95% Clopper-Pearson confidence intervals will be provided.

For the analysis after Year 6, the proportion of women with clinical change in bleeding profile regarding HMB **after Year 5 until the end of Year 6** will be analyzed.

CCI
[Redacted text block]

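### HMB cut-off: the definition of clinical change includes a loss of exactly 80 mL, but the visible numerator and denominator lists count only losses above 80 mL

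*Protocol*

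**What the plan says.** The new text in protocol Section 15.1.2.31 first gives a definition. A finding of no clinical change requires a value below the cut at every assessment: "volume of blood loss was < 80mL at the beginning of Year 6 and remained < 80mL at the end of Years 6, 7 and" (that sentence ends by naming the eighth year). Clinical change is the complement, a loss of at least "80mL at the beginning of Year 6 or at end of Years 6, 7 or 8, respectively". SAP Section 6.2.2.2 repeats this rule for clinical change: "the volume of blood loss was ≥ 80mL at the beginning of Year 6 or at end of Years 6, 7 or 8". The list of secondary variables in protocol Section 10.3.1.1.2 uses the same cut: "Categorized menstrual blood loss (MBL) (≥ 80 ml per 30 days) at end of Year 6, 7 and 8".

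The same new text then lists who enters the denominator and numerator at each analysis. The second denominator line for Year 6 is "Baseline MBL not >80mL/30days and End of Year 6 MBL assessment available". The numerator entries are of the form "End of Year 6 MBL>80mL/30days" and, for the next analysis, "End of Year 7 MBL>80mL/30days". The Year 8 lists follow the same pattern. None of the visible lists uses ≥.

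Success requires fewer than 20% of the HMB subgroup with a clinical change and an upper 95% Clopper-Pearson limit of at most 35% (protocol Section 10.3.2.2 and Section 15.1.2.31). The target size of the subgroup is 36 women (protocol Section 5).

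**The concern.** Two rules for the same classification stand a few lines apart and disagree at one value. The definition and the lists are both new text of Amendment 1, so this is not a difference between superseded and current wording. The success sentence points back to the definition, whereas the proportion it judges is built from the lists, so a programmer could defend either rule.

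This cut-off feeds the only success rule visible in the documents. The subgroup is small, and the SAP's document history (Section 7, entry for v2.0) already records a low number of HMB subjects. The disagreement runs in one direction: wherever the rules differ, the lists give the lower proportion with a change. A choice between them made after the volumes are known would be hard to defend, however rare the case.

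**Working it through.** **Inputs.** Target subgroup: 10% of 360 = 36 (protocol Section 5), which reproduces the stated figure. Success rule: x/n < 20% and upper two-sided 95% Clopper-Pearson limit ≤ 35%. The documents do not give the evaluable n, the resolution of the stored volumes or the distribution of volumes. Those are assumptions below.

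**Step 1: the two rules side by side (Year 6 analysis; 50 mL stands for any value clearly below the cut).**

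| Baseline, end of Year 6 | Definition | In denominator list | In numerator list |
|---|---|---|---|
| 79.9 mL, 50 mL | no change | yes | no |
| 80 mL, 50 mL | change | yes | no |
| 50 mL, 80 mL | change | yes | no |
| 80 mL, missing | change | no | no |
| 80.1 mL, 50 mL | change | yes | yes |

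The rules agree just below and just above 80 mL and differ only at 80 mL. In the fourth row the woman is dropped as if lost to follow-up without a preceding change, although by the definition she had one.

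**Step 2: what one woman does to the decision.** The upper limit is the 0.975 quantile of Beta(x+1, n−x).

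- n = 36: 6/36 = 16.7%, upper limit 32.8%, pass. 7/36 = 19.4%, upper limit 36.0%, fail.
- n = 20 (assumed): 2/20 has upper limit 31.7%, pass. 3/20 has 37.9%, fail.
- At assumed n of 25 and 30, the largest passing counts are 3 and 5.
- Fourth-row case: the lists give 6/35 (upper limit 33.6%, pass) and the definition gives 7/36 (fail).

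**Step 3: how likely a tie is.** Assume a share s = 3% to 10% of W = 80 to 120 collection windows lies evenly between 60 and 100 mL, a range 40 mL wide, with storage resolution r. Then P(at least one window equals 80) = 1 − (1 − s·r/40)^W.

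- r = 1 mL: 1 − (1 − 0.00075)^80 = 5.8%, up to 1 − (1 − 0.0025)^120 = 25.9%.
- r = 0.1 mL: 1 − (1 − 0.000075)^80 = 0.6%, up to 1 − (1 − 0.00025)^120 = 3.0%.

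**Step 4: how likely a reversal is.** At n = 36 a tie reverses the conclusion only if exactly 6 of the other 35 women have a change. The binomial probability of that is largest at a change rate of 6/35, where it is about 0.18. At a 10% change rate it is about 0.08. Treating the two events as roughly independent:

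- whole mL: at most 0.259 × 0.18 ≈ 0.047, about 5%.
- 0.1 mL: at most 0.030 × 0.18 ≈ 0.005, about 0.5%.

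**Step 5: why the repair must keep the word not.** Read literally, not >80 is also satisfied by a missing earlier window, because only the last assessment is required to be available. Windows can be missing: SAP Section 6.2.2.1 invalidates any with fewer than 20 solid observations. If not >80 became <80, a woman with no valid baseline but a valid end-of-Year-6 volume would leave the Year 6 denominator. If that volume were 80 mL or more she would still be in the numerator. Losing three unchanged women this way would turn 6/36 (upper limit 32.8%, pass) into 6/33 (35.5%, fail).

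**The case against.** Four arguments weigh against the point.

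- **The documents already indicate the answer.** The success sentence refers to the definition, and every visible statement outside the lists uses ≥80 or <80. This stands as evidence of intent and makes the fix easy to choose. It does not remove the contradiction, because the lists are the counting instructions.
- **The operative lists cannot be seen.** They are redacted in the protocol body and in SAP Section 6.2.2.2. This stands. A reader might infer that the SAP analysis itself counts only losses above 80 mL, but the documents do not show that. The visible SAP history records only a terminology correction for that section. That neither confirms nor excludes a corrected sign.
- **The strict sign may be a reading error.** The amendment underlines additions, and an underlined > resembles ≥. This cannot be excluded from the extracted text, and a look at the source page would settle it.
- **An exact 80 is remote.** The volume is a sum over products and days, adjusted for the length of the analysis period where needed. This stands for unrounded volumes and is why the point is minor.

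Two stronger readings are tempting. One is that every woman at exactly 80 mL becomes a success under the lists. That holds only if she is evaluable; the woman with baseline 80 mL and no Year 6 value is excluded instead. The other is to take the tie probability of 6% to 26% as the risk to the conclusion. It is not, because the count must also be at the boundary.

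**Conclusion.** The inconsistency is real and minor. In the visible current text, the definition of clinical change includes 80 mL and the counting lists for Years 6, 7 and 8 do not. An individual classification changes only for a woman at exactly 80 mL, and the lists then favour success. The conclusion reverses only if the count is also at the boundary.

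At n = 36 the chance of reversal is at most about 5% with whole-mL storage and about 0.5% at 0.1 mL. These ceilings rest on the assumed share and spread of volumes near the cut, 80 to 120 windows, rough independence and the least favourable change rate; at a 10% change rate they are less than half as large. Nothing visible shows that the SAP's own lists carry the same sign, and the Pearl Index analysis is not affected.

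**What to change.** In the numerator and denominator lists for Years 6, 7 and 8, replace >80 mL per 30 days by ≥80 mL per 30 days, and replace not >80 by not ≥80. Do not use <80 for the second, since that would change how missing earlier windows are handled. State that the cut-off is applied to the unrounded cumulative volume. Confirm that the redacted lists in SAP Section 6.2.2.2 use the same sign, and align them if they do not.

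The cost is wording only, with no new data. No result changes unless a woman is at exactly 80 mL, in which case the proportion with a change can rise by that woman.
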